2.5.3 Handling of missing values/censoring/discontinuations

There will be no imputation for missing data at Week 4, and the primary analysis will be based on only observed data.

2.5.4 Supportive analyses

Not Applicable.

2.6 Analysis of the key secondary objective

Not Applicable.

2.6.1 Key secondary endpoint

Not Applicable.

2.6.2 Statistical hypothesis, model, and method of analysis

Not Applicable.

2.6.3 Handling of missing values/censoring/discontinuations

Not Applicable.

2.7 Analysis of secondary efficacy objectives

All secondary efficacy analysis will be provided for safety set.

2.7.1 Secondary endpoints

The secondary effectiveness variables are the changes in FEV₁ % predicted, CFU and LCI and it's comparison among themselves at respective visit will be performed for safety set.

2.7.1.1 Changes in FEV₁ % predicted from baseline to Week 4

The changes from baseline in FEV₁ % predicted to each post-baseline visit will be analyzed in a similar manner as the primary variable, i.e.

- The FEV₁ % predicted and it's mean change from baseline to each post-baseline visit will be summarized using descriptive statistics (n, mean, standard deviation, median, minimum and maximum).
- Between visits comparison for changes in FEV₁ % predicted from baseline will be analyzed in similar manner as primary variable. Estimates change over time will be presented as LS-Means, pairwise LS-Mean differences along with 95% confidence intervals and two sided p-values for the pairwise differences between visits.

2.7.1.2 Changes in CFU (/mL) from baseline to Week 4

The changes from baseline in CFU (/mL) to each post-baseline visit will be analyzed in a similar manner as the primary variable, i.e.

- The CFU and it's mean change from baseline to each post-baseline visit will be summarized using descriptive statistics (n, mean, standard deviation, median, minimum and maximum).
- Between visits comparison for change in CFU from baseline will be analyzed in similar manner as primary variable. Estimates change over time will be presented as LS-Means with 95% confidence intervals and two sided p-values for the pairwise differences between visits.

2.7.1.3 Change in LCI from baseline to Week 1

This analysis is contained in the ANOVA model for LCI described above.

2.7.1.4 Changes in LCI, FEV₁ % predicted, CFU between Week 4 and Week 8

This analysis is contained in the ANOVA models described above.

2.7.1.5 Correlation between change from baseline in LCI, FEV1 % predicted, CFU at Week 1, Week 4 and Week 8

Correlation based on change in FEV1 % predicted, CFU and LCI will be evaluated for each pair using Karl Pearson correlation coefficient. Visit 2 will be considered as baseline. If baseline value is missing then change is taken from the data recorded at screening. Change from baseline will be calculated as value at post-baseline minus value at baseline. Estimates as Karl Pearson correlation coefficient with their 95% confidence intervals and p-values will be presented. Additionally, the correlation among each pairs will be explored using scatterplots for raw values as well as for changes at respective visit.

All subject efficacy data including FEV1, predicted FEV1, FRC, LCI by multiple breath washouts, CFU (quantitative density) will be listed by age group, treatment dose form and visit(as applicable) along with date of assessment for safety set.

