#### **7.4.3 Microbiological assessment**

For microbiological assessment, sputum will be collected in sterile containers. If a patient is unable to expectorate, a deep-throat cough swab may be collected or sputum may be induced at the investigator's discretion. Sputum will be cultured for the presence of *P. aeruginosa* (quantitative test) and *B. cepacia complex*. Deep-throat cough swab specimens will be evaluated qualitatively only.

Tobramycin MIC values for *P. aeruginosa* will be determined for specimens obtained at the visits listed previously to assess change in pathogen susceptibility to applied study drug before and after the treatment.

Microbiological assessment will be performed in a central laboratory.

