### **10.5 Analysis of secondary objectives**

#### **10.5.1 Efficacy (secondary)**

FEV1 and CFU will be analyzed analogously to LCI, the correlation between FEV1, CFU and LCI will be explored using scatterplots (for raw values as well as for changes). The correlation coefficients will be calculated together with their 95% confidence intervals and p-values. All other secondary and exploratory endpoints will be analyzed descriptively.

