CF Patients chronically infected with *P. aeruginosa* on regular antipseudomonal standard inhalation therapy in an on / off regimen are showing well characterized differences in FEV1 between on and off-cycles (Ramsey et al 1999; Konstan et al 2011a). Thus, this population allows an evaluation of LCI based on these intraindividually observed FEV1 alterations, without any changes to their standard therapy.

The microbiology parameter “colony forming units” of pseudomonas aeruginosa has been selected as a third efficacy marker to be compared with LCI as well, because spirometry (FEV1) strongly depends on daily performance and compliance to spirometry of the patient. LCI and FEV1, respectively, should reflect alterations in bacterial colonization.

The study duration of 8 weeks comprises a complete on / off treatment cycle starting with 28 days inhalation followed by 28 days without Study drug inhalation. This design allows to obtain baseline lung function at start of the inhalation cycle (representing minimal lung function at the end of the inhalation pause), the development/improvement of lung function after 1 and after 4 weeks of inhalation therapy (representing maximal lung function) and the subsequent decline in lung function after 4 weeks of cessation of inhalation therapy. The detected intraindividual differences between best and worst lung function then allow to compare LCI and FEV1 results and to assess feasibility of LCI as primary surrogate outcome parameter in future clinical studies.

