2.7.2 Handling of missing values/censoring/discontinuations

Missing data will not be imputed and the secondary analysis will be based on only observed data.

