The change in FEV1 % predicted, CFU and LCI from baseline to Visit 3(Week1) will be calculated using the formula as Change= value at Week 1 – value at baseline. Visit 2 will be considered as baseline. If baseline value is missing then change is taken from the data recorded at screening. Analysis will be performed based on observed data.

- Summary of FEV1 % predicted, CFU and LCI at baseline and at Visit 3(Week1) for both groups will be presented standard descriptive statistics (n, mean, standard deviation, median, minimum and maximum).

- The mean changes in FEV1 % predicted, CFU, and LCI from baseline to visit 3 (week 1) will be displayed for both groups.

Comparisons of changes in FEV1 % predicted, CFU and LCI from baseline to visit 3 will be done based on descriptive statistics. Analysis will be done on safety set.

2.13.1.4 Change in air trapping (FRC_{ples} - FRC_{MBW}) from baseline to Week 1, Week 4 and Week 8.

Air trapping will be assessed by the difference in FRC measured by bodyplethysmography (FRC_{ples}) and FRC measured by MBW (FRC_{MBW}). The air trapping (FRC_{ples} - FRC_{MBW}) and its change from baseline to each post-baseline visit will be summarized by descriptive statistics (n, mean, standard deviation, median, minimum and maximum). The change in air trapping from baseline will be calculated using as Change= Value at post-baseline – value at baseline. Visit 2 will be considered as baseline. If baseline value is missing then change is taken from the data recorded at screening. Analysis will be performed based on observed data for safety set.

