5.4.2 Secondary analysis

The SAS procedure PROC MIXED will be used for this analysis of FEV1 and CFU with the following code:

Model: FEV1 = Visit + patients + error.

```
proc mixed data=<....> method=reml;
  where visit in (2, 3, 4, 5);
  class visit usubjid;
  model fev1= visit ;
  repeated visit/subject=usubjid type=un;
  lsmeans visit /pdiff cl;
  estimate "FEV1 at Baseline vs FEV1 at Visit 3" -1 1 0 0 /cl alpha=0.05;
  estimate "FEV1 at Baseline vs FEV1 at Visit 4" -1 0 1 0 /cl alpha=0.05;
  estimate "FEV1 at Baseline vs FEV1 at Visit 5" -1 0 0 1 /cl alpha=0.05;
  estimate "FEV1 at Visit 3 vs FEV1 at Visit 4" 0 1 -1 0 /cl alpha=0.05;
  estimate "FEV1 at Visit 3 vs FEV1 at Visit 5" 0 1 0 -1 /cl alpha=0.05;
  estimate "FEV1 at Visit 4 vs FEV1 at Visit 5" 0 0 1 -1 /cl alpha=0.05;
  ods output lsmeans=lsm diffss=diff1;
run;
where,
fev1= FEV1 at each visit,
subjid=Patient ID.
```

Pearson correlation coefficient among the pairs based on the change from baseline in LCI, FEV1 and CFU after 1 week, 4 weeks, and 8 weeks

The SAS procedure CORR will be used to compute this coefficient with the following code:

```
proc corr data= <.....> pearson fisher;
  var var1;
  with var2;
  ods output FisherPearsonCorr=cor;
  ods output PearsonCorr=correl;
run;
```

where, var1 and var2 are two different variables measured on the same patient.

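### CFU/mL is analysed on the raw scale, so a few high-count patients can dominate the CFU changes and correlations

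*SAP*

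**What the plan says.** Protocol 10.5.1 gives the general rule for the secondary endpoints: FEV1 "and CFU will be analyzed analogously to LCI". SAP 2.7.1.2 keeps to it, with the unit stated: "The changes from baseline in CFU (/mL) to each post-baseline visit will be analyzed in a similar manner as the primary variable". That means n, mean, SD, median, minimum and maximum of the value and its change, then LS-means, 95% confidence intervals and two-sided p-values for visit differences. SAP 2.7.1.4 takes the Week 4 to Week 8 CFU change from the same model.

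SAP 5.4.2 supplies the PROC MIXED program, which "will be used for this analysis of FEV1 and CFU with the following code"; the response is entered as measured.

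For the correlations, SAP 2.7.1.5 says: "Correlation based on change in FEV1 % predicted, CFU and LCI will be evaluated for each pair", by Pearson's coefficient. Change is a simple difference, post-baseline minus baseline, and the correlation code in SAP 5.4.2 requests only Pearson with a Fisher interval. SAP 2.13.1.3 tabulates mean CFU change to Week 1 on the same scale.

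On incomplete data, SAP 2.7.2 says: "Missing data will not be imputed and the secondary analysis will be based on only observed data". SAP Section 4 lists two departures from the protocol (the safety set and FEV1 % predicted); neither concerns the CFU scale. Protocol 7.4.3 adds: "Deep-throat cough swab specimens will be evaluated qualitatively only".

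**The concern.** Bacterial counts range over orders of magnitude, and treatment acts on them roughly by a factor. Raw differences give each patient a weight proportional to the starting count. The mean change, its standard error and the Pearson coefficient can then be set by the few patients with the highest counts, while equal proportional responses in the others hardly register. The normal-theory interval may also cover poorly at this sample size.

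This bears on stated objectives. Protocol Section 11 says CFU "has been selected as a third efficacy marker to be compared with LCI as well", partly because spirometry depends on the patient's performance, and it expects LCI and FEV1 to follow bacterial colonisation. CFU appears in the secondary objectives on change to Week 4, change from Week 4 to Week 8, and correlation with LCI and FEV1. A null CFU change or a weak CFU–LCI correlation could be read as no microbiological response, or as LCI failing to track bacterial load, when the cause is the scale.

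**Working it through.** **The plan's own figure.** Protocol 10.7 assumes an FEV1 change of 5% with intraindividual SD 9%, two-sided 5%, power 80%. With d = 5/9 = 0.556, a paired t-test (noncentral t) has power 79.3% at n = 27 and 80.9% at n = 28. So 28 reproduces, and 28/(1 − 0.20) = 35. This figure concerns FEV1 only. Protocol 10.8 gives no power for secondary variables, and no CFU mean, SD, expected fall or assay limit is stated.

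**Weights on the raw scale.** A tenfold fall from 10^8 is 10^8 − 10^7 = 9×10^7. A tenfold fall from 10^5 is 10^5 − 10^4 = 9×10^4. The ratio is 1,000, although both are 1 log10.

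**Simulation.** Everything about CFU here is an assumption.
- log10 CFU at baseline = m + b + e1; at Week 4 = m − fall + b + e2. The between-patient SD (of b) is 1, 1.5 or 2; the within-patient SD (of e1 and e2) is 0.7 or 1.0.
- The SD of the log10 change is √2 × the within-patient SD: 0.99 or 1.41. A 1-log10 fall is then a standardised effect of 1.01 or 0.71 before any ceiling.
- Baseline mean m is 6.5 or 7.5. Counts are capped at 10^8, at 10^9 or not at all.
- n = 28, 4,000 replicates, paired t-test on raw and on log10 changes. With complete data this equals a pairwise visit contrast under the unstructured covariance of SAP 5.4.2.

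Results for a true 1-log10 fall, as ranges over the SDs:

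| Setting | Power, raw | Power, log10 | Coverage of raw 95% CI | Median share of absolute raw change from top two patients |
|---|---|---|---|---|
| (a) mean 6.5, no ceiling | 2–25% | 95–100% | 4–42% | 71–94% |
| (b) mean 6.5, ceiling 10^9 | 24–46% | 94–100% | 78–93% | 51–66% |
| (c) mean 7.5, ceiling 10^9 | 54–81% | 90–100% | 91–94% | 33–41% |
| (d) mean 6.5–7.5, ceiling 10^8 | 54–96% | 87–100% | 92–95% | 20–40% |

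With equal weights, two of 28 patients would supply 2/28 = 7%.

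- **Smaller fall.** For 0.5 log10, over all these settings: 1–50% raw, 30–74% log10.
- **Other sample sizes, 1-log10 fall.** At n = 20, as could happen if some patients give swabs only (no ceiling, 10^9, or 10^8 with mean 6.5): 2–62% raw, 79–99% log10. At n = 35 with ceiling 10^9: 35–90% raw, 97–100% log10.
- **Correlation.** A true r of −0.5 between log10 CFU change and FEV1 change averages −0.10 to −0.36 on raw changes (power 7–50%) and −0.37 to −0.50 on log10 changes (power 53–81%). Spearman on raw changes averages −0.26 to −0.38, and on log10 changes −0.35 to −0.47. Ranking the raw changes does not remove the attenuation, because a raw change still mixes starting level with response.

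**Second set of assumptions.** Baseline mean 7, no ceiling, the same standardised effect as FEV1 (5/9), SD of the log10 change 0.9. At n = 28, log10 power is about 81%. Raw power is 26%, 9% and 4% for between-patient SD 0.5, 1.0 and 1.5. The loss is small only when counts hardly vary: with no between-patient spread and a change SD of 0.25 log10, raw power is 77% against 81%.

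**Below-detection value.** Moving the substituted value shifts the mean log10 change by the log10 ratio of the two values times the rise in the proportion below the limit. With mean 6.5, SDs 2 and 1.0 and a limit of 10^3, the total SD is √5 = 2.24. The proportion below is Φ(−3.5/2.24) = 6% at baseline and Φ(−2.5/2.24) = 13% at Week 4, a rise of 0.07. Limit versus half the limit: 0.30 × 0.07 = 0.02. Limit versus 1 CFU/mL: 3 × 0.07, about 0.2.

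**The case against.** The text is not in dispute; the challenge is to the size.

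- **The unbounded case is extreme.** In (a) the expected arithmetic mean count is 10^(6.5 + 1.151 × total variance): 10^8.2 at the narrowest SDs (variance 1.49) and 10^12.3 at the widest (variance 5). The 2% power and 4% coverage rest on that tail. This stands: (a) is a worst case, and (b) to (d) carry the argument.
- **With a ceiling the loss can be moderate.** At mean 7.5, ceiling 10^8 and SDs of 1 and 0.7, power is 96% raw against 100% log10, and raw coverage in (d) is close to nominal. This also stands. A sharp loss of power is possible, not certain.
- **The model favours log10 by construction**, since the data are normal on that scale and the true correlation is defined there. That is fair, but a multiplicative model is the natural one for counts spanning orders of magnitude, and log10 had the higher power in every setting run.
- **CFU is unpowered, and skew would be visible.** No success rule depends on a CFU p-value, SAP 2.13.1.3 is descriptive only, and medians, scatterplots and listings are planned. This limits the severity. But intervals and p-values are still planned, and seeing the skew does not correct them.
- **Log10 needs an arbitrary below-detection value.** True, and substituting 1 CFU/mL would move the mean by about 0.2. That is the reason to fix the value in advance.

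**Conclusion.** The concern holds. Followed as written, the plan gives CFU estimates, intervals, p-values and correlations that a few high-count patients can dominate. That CFU is left untransformed, with no below-detection rule, is certain from the text. How much it matters is not, because the documents give no CFU distribution. Under the assumed bounded settings and a 1-log10 fall, raw power ranges from 24% to 96% against 87–100% on log10, and the top two of 28 patients supply 20–66% of the absolute change. Without a ceiling it is far worse; if counts hardly vary it is negligible.

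The damage is confined to secondary and exploratory CFU results. The primary LCI analysis, the FEV1 analysis, the LCI–FEV1 correlation and the sample size of 28/35 are unaffected. It should be fixed before analysis, but it does not threaten the trial's main conclusion.

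**What to change.** Before analysis, amend the SAP as follows:

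- Use log10(CFU/mL) for the CFU summaries, the mixed model and the Pearson correlations (SAP 2.7.1.2, 2.7.1.4, 2.7.1.5, 2.13.1.3 and 5.4.2), and record the change in SAP Section 4.
- Back-transform visit contrasts and their intervals to geometric mean ratios.
- State one substitution value for quantitative cultures below the detection limit, check a second value, and say that these are observed results, not missing data under SAP 2.7.2.
- Add Spearman correlation of the log10 changes as a sensitivity analysis.
- Report the number of quantitative cultures at each visit, since swabs give no count.
- If the *P. aeruginosa* entry among the laboratory parameters (Laboratory data, under SAP 2.8.2) is the same count, put it on the same scale.

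The cost is SAP wording and one derived variable; no new data are needed. The one downside is the somewhat arbitrary below-detection value. With an assumed limit of 10^2 or 10^3/mL and up to 13% of Week 4 counts below it, choosing the limit or half the limit changed the mean log10 change by at most about 0.03, and log10 power stayed at 92–100%. Far lower values such as 1 CFU/mL matter more.

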2.7.2 Handling of missing values/censoring/discontinuations

Missing data will not be imputed and the secondary analysis will be based on only observed data.

2.8 Safety analyses

Safety analysis including TEAE, vital sign, lab parameter and it's change from baseline will be evaluated based on safety set. All listings will be ordered according to age categories 6 to 12, >12 to 17 and >17 for safety set.

2.8.1 Adverse events (AEs)

The verbatim term recorded on CRF will be identified as adverse event and will be coded by primary system organ class and preferred term using Medical Dictionary for Regulatory Activities (MedDRA) version 18.1 and above, and other version used for coding. Adverse events starting on or after the time of the first inhalation of study drug but not later than 7 days (30 days in the case of a SAE) after the date of last dose of study drug taken or those AE present at baseline with increased severity will be classified as a treatment emergent adverse event and will be included in all summaries. AEs which started and ended prior to baseline and AEs which started prior to baseline but whose severity does not change post baseline will not be included in treatment emergent adverse event.

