# **8 Safety monitoring**

## **8.1 Adverse events**

### **8.1.1 Adverse event definition and reporting**

An adverse event is the appearance or worsening of any undesirable sign, symptom, or medical condition occurring after signing of informed consent, even if the event is not considered to be related to the diagnostic method of the study.

Medical conditions/diseases present before first intake of study drug are only considered adverse events if they worsen after study start. Abnormal laboratory values or test results constitute adverse events only if they induce clinical signs or symptoms, require dose reduction or temporary or permanent study drug discontinuation or require therapy. All adverse events with a date of onset up to 30 days following the last dose of study drug/the last study examination must be reported.

The occurrence of adverse events should be sought by non-directive questioning of the patient and his/her parents (for minors) at each visit during the study. Adverse events also may be detected when they are volunteered by the patient during or between visits or through physical examination, laboratory test, or other assessments. All adverse events must be recorded on the Adverse Events CRF with the following information:

1. the severity grade (mild, moderate, severe)
2. its relationship to the study drug(s) (suspected/not suspected)
3. its duration (start and end dates or if continuing at final exam)
4. whether it constitutes a serious adverse event (SAE)

All adverse events should be treated appropriately. Treatment may include one or more of the following: no action taken (i.e. further observation only); study drug or study diagnostic method dosage adjusted/temporarily interrupted; study drug or study diagnostic method permanently discontinued due to this adverse event; concomitant medication given; non-drug therapy given; patient hospitalized/patient's hospitalization prolonged. The action taken to treat the adverse event should be recorded on the Adverse Event CRF.

Once an adverse event is detected, it should be followed until its resolution or until it is judged to be permanent, and assessment should be made at each visit (or more frequently, if necessary) of any changes in severity, seriousness, the suspected relationship to study drug or the diagnostic method, the interventions required to treat it, and the outcome.

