### **8.4      Reporting of adverse events and pregnancies after the last dose of study drug taken**

All AEs, SAEs, and pregnancies which occurred within 30 days after last intake of last dose of study drug should be reported. After this 30-day period, only SAEs, and pregnancies should be reported until the last visit.

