#### **10.5.2 Safety**

Safety assessments will be based mainly on the frequency of adverse events. Adverse events will be coded by primary system organ class and preferred term according to the Medical Dictionary for Regulatory Activities (MedDRA). All AEs will be assigned to the last treatment the patient received before AE start. In the data listings of adverse events, the severity of an AE, whether or not an AE is related to MBW or study drug, and whether or not it is a serious AE, will be indicated. An adverse event related to study drug is defined as one considered by the investigator to have a suspected relationship with the diagnostic method or the study drug. The adverse events will be summarized by the number and percentage of patients in each primary system organ class and preferred term. For summaries by severity of event, the most severe occurrence for a particular preferred term will be used for a given patient. Summary tables of adverse events by treatment and severity will be provided. Multiple occurrences of the same AE or SAE in the same patient in one treatment period will be counted only once, using the worst severity and drug relationship. Data from other tests (e.g. electrocardiogram or vital signs) will be listed, notable values will be flagged, and any other information collected will be listed as appropriate.

Vital signs data will be listed, including change from baseline.

All laboratory data (blood chemistry) will be listed with abnormal values flagged. The laboratory values will be summarized. Incidence of newly occurring or worsening notably abnormal laboratory values will be produced.

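### SAP 2.8.1 keeps new non-serious AEs that start more than 7 days after the last dose out of every AE summary it describes, and SAP section 4 does not declare this narrowing of protocol 10.5.2

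*SAP*

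**What the plan says.** SAP 2.8.1 defines a treatment-emergent AE (TEAE) as one starting from the first inhalation and "not later than 7 days (30 days in the case of a SAE) after the date of last dose of study drug taken", or one present at baseline that becomes more severe. Such an event "will be classified as a treatment emergent adverse event and will be included in all summaries". The tables in SAP 2.8.1.1 and 2.8.2 are all worded as TEAE tables: SOC/PT, severity, relationship, discontinuation of drug, action taken, additional therapy, outcome, serious, special interest and death. The one AE output without that restriction that would show a late non-serious event is the listing of all AEs at the end of SAP 2.8.1.1.

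Protocol 10.5.2 has neither a TEAE concept nor an onset cut-off. It says "The adverse events will be summarized by the number and percentage of patients in each primary system organ class and preferred term" and "Summary tables of adverse events by treatment and severity will be provided". On attribution it says "All AEs will be assigned to the last treatment the patient received before AE start".

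On collection, protocol 8.1.1 requires reporting of "All adverse events with a date of onset up to 30 days following the last dose of study drug" (or the last study examination). Protocol 8.4 says "All AEs, SAEs, and pregnancies which occurred within 30 days after last intake of last dose of study drug should be reported". The AE CRF items in 8.1.1 include severity, relationship to study drug and "its duration (start and end dates or if continuing at final exam".

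SAP section 4 lists two changes from the protocol: the safety set definition, and FEV1 % predicted in place of FEV1 in litres. The AE window is not among them.

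**The concern.** The study runs one on-phase of 28 days and one off-phase of 28 days, so half of the planned follow-up is off drug. A cut-off 7 days after the last dose removes most of that half from AE tabulation, although the AEs are collected throughout it. The protocol's own attribution rule has no lag limit. Under it, a new non-serious event on Day 45 belongs to tobramycin and would be counted.

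Two things follow. The SAP tables do not give counts by SOC/PT and severity for non-serious events that the protocol's summary would include; a reader would have to count them by hand from a listing. And the narrowing is not recorded where the SAP records its departures from the protocol. Efficacy is not at stake.

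**Working it through.** Inputs:
- Day 1 is the day of the first dose, and the on-phase is 28 days (SAP 2.1.1), so the nominal last dose is on Day 28.
- Visit 5 is on Day 56, minus up to 3 days (protocol Table 7-1), so Day 53 to Day 56.
- The TEAE limit is last dose + 7 days for non-serious events and + 30 days for SAEs (SAP 2.8.1).
- The AE reporting limit is last dose + 30 days (protocol 8.4).

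The plan states no figure of its own to reproduce here. The check is calendar arithmetic:
- cut-off day = last-dose day + 7
- days outside the tables = Visit 5 day − cut-off day
- share of follow-up = days outside ÷ Visit 5 day

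| Last dose | Cut-off | Visit 5 | Days outside | Share of follow-up |
|---|---|---|---|---|
| Day 28 | 28 + 7 = 35 | Day 56 | 56 − 35 = 21 | 21/56 = 37.5% |
| Day 28 | 35 | Day 53 | 53 − 35 = 18 | 18/53 = 34.0% |
| Day 31 (assumed) | 31 + 7 = 38 | Day 56 | 56 − 38 = 18 | 18/56 = 32.1% |
| Day 31 (assumed) | 38 | Day 53 | 53 − 38 = 15 | 15/53 = 28.3% |
| Day 25 (assumed) | 25 + 7 = 32 | Day 56 | 56 − 32 = 24 | 24/56 = 42.9% |

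Day 31 supposes that a 3-day interruption is made up at the end of the cycle. Day 25 supposes that the last dose is taken 3 days early.

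As a share of the off-phase with the last dose on Day 28: 21 of Days 29 to 56 (28 days) = 75%; with Visit 5 on Day 53, 18 of Days 29 to 53 (25 days) = 72%.

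Reporting and SAE limit: 28 + 30 = Day 58, after Visit 5. AEs on Days 36 to 56 are therefore collected, and SAEs up to Visit 5 stay in the tables. With the last dose on Day 25 the SAE limit is 25 + 30 = Day 55, one day before a Day 56 visit.

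Where a new non-serious AE starting on Day 45 would go, with the last dose on Day 28:
- Protocol 10.5.2: assigned to tobramycin and counted by SOC/PT and by severity.
- SAP 2.8.1 and 2.8.1.1: 45 is later than 35, so it is not a TEAE, is in no AE summary, and is in the all-AE listing.
- SAP section 4: no entry to explain the difference.

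**The case against.** The best defence is that protocol 10.5.2 gives no onset window at all, so an SAP that defines treatment emergence fills a gap and does not contradict anything. A 7-day window is also a defensible choice for attributing events to the drug. Both points have force. They do not explain why there is no summary of the remaining events, given that the protocol attributes all AEs without a lag limit and that the events are collected. A listing is not the tabulation the protocol describes.

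The defence is also right that the practical loss is small. No data are lost: the listing carries coded terms, dates, severity, relationship, seriousness and outcome, and only 35 patients are planned. Study discontinuations with their reasons (SAP 2.3.1), concomitant medication up to the last visit (SAP 2.4.3) and Visit 5 creatinine and BUN (SAP 2.8.2) are all reported elsewhere.

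Four stronger readings that a reader might infer are not supported:
- That the protocol promises AE counts for the whole study. It states no cut-off, but it does not state that period either.
- That about a third of AEs are lost. The documents give no AE rate. The tables also count a patient once per PT and once per SOC, so a late event may add nothing to them.
- That MBW-related events at Visit 5 go unreported. The pooled table of events related to the diagnostic method or the study drug does omit new non-serious events starting at that visit. But the SAP sets its suspected flag from the study-drug relationship item at every visit, and relation to MBW is already in the listing, which is where protocol 10.5.2 asks for it. This is secondary.
- That the 7-day window breaches the 30-day rule in protocol 8.1.1 and 8.4. Those are reporting rules, not a definition of treatment emergence.

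**Conclusion.** The point holds as a minor one. In the SAP text, new non-serious AEs starting after last dose + 7 days are in no AE summary, protocol 10.5.2 has no such limit, and SAP section 4 is silent.

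With the last dose on Day 28, 34% to 37.5% of follow-up days lie outside the tables, depending on the date of Visit 5. The figure is 28% to 32% if the last dose moves to Day 31, and 43% if it is on Day 25 with Visit 5 on Day 56. These are scenarios and not bounds, and they measure days, not AEs or table counts.

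Unaffected are SAEs up to Visit 5 on the nominal schedule, efficacy and the laboratory summaries. Baseline AEs that worsen are also still counted, reading the SAP as setting no time limit for them. A patient who stops early and has the discontinuation visit within 7 days of the last dose loses nothing.

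The conclusion rests on the SAP text alone. The mock tables and the output list to which the SAP refers were not available, and one of them might already contain an all-AE summary.

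**What to change.** Keep the 7-day TEAE tables as the on-drug summary. Add one SOC/PT summary of all AEs from first dose to Visit 5, by maximum severity and by relationship as recorded, with onset after last dose + 7 days shown separately. Record the 7-day window and the reason for it in SAP section 4.

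The cost is one or two extra tables, which will be sparse, slightly higher AE counts than the TEAE tables show, and one entry in section 4. No new data are needed, because onset date, severity and relationship to study drug are already AE CRF items under protocol 8.1.1.
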